The loss to follow-up at the termination visit is assumed to be 10%. The proportion missing at the 3-year termination visit reported in HPT is 8.6% over all treatment groups (38). In addition, subjects will be censored due to the development of hypertension. The incidence of hypertension (DBP ≥90 mmHg or taking antihypertensive medication) among high weight controls in HPT (38) is 30.2%. The Phase I data are consistent with this. Among high weight controls with initial DBP of 83-89 mmHg, the incidence is 12.5% after 12 months, or 33.0% extrapolating to 3 years. Using the incidence rate of 30.2% and the treatment effect estimates described below, we would expect an average incidence of hypertension of 23.4%. Combining this with the 10% loss to follow-up yields an average percent censored for blood pressure measurement at the termination visit of 31.1%. This is a conservative estimate since the incidence of hypertension reported in HPT may be

high because only one visit was used. Also, not all those with DBP readings above 90 mmHg will go on to take antihypertensive medication, and many subjects who do will have provided at least partial data, especially in the analysis using all follow-up data.

- 3. The power to detect a difference in mean DBP change of 1.5 mmHg between combined intervention and control groups should be 80%.
- 4. A Bonferoni adjustment is made based on the fact that 3 comparisons will be examined.
- 5. The sample size is calculated from the following formula:

$$N= 2\sigma^2 (z_{\alpha} + z_{\beta})^2 / \Delta^2 (1 - P_c)$$

where N = number in each group

 Δ = difference in DBP change between the 2 groups

 $\sigma^2 = V(x_2-x_1)$ or $V(x_3 - x_1)$ as described above

P_c = average percent censored

 $Z_{\alpha} = 2.394$

 $Z_{\beta} = 0.84$

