Furthermore, at its meeting of September 16, 1992, the Data and Safety Monitoring Committee recommended that safety monitoring be performed for systolic blood pressure of 140-159 mmHg just as for diastolic blood pressure $_{\geq}90$ mmHg or systolic blood pressure $_{\geq}160$ mmHg. This followed the availability of a draft of the JNCV report which labeled systolic blood pressure of 140-159 mmHg as Stage I hypertension. The recommendation was approved by the Steering Committee on September 29, 1992.

Sample size calculations for having diastolic blood pressure $_{\geq}90$ mmHg or taking antihypertensive medication are presented first and are based on the following assumptions:

- 1. Power is computed using two estimates of the event rate (DBP $_{\geq}90$ or on hypertensive medication) over an average 3.5 years of follow-up:
 - a. The rate reported among the high weight controls in HPT (38) for the same endpoint is 30.2% over 3 years of follow-up. This was calculated as a proportion of all participants, and thus takes loss to follow-up into account. The data from Phase I of TOHP are consistent with this estimate. Among high weight controls with initial DBP's of 83-89 mmHg the incidence of hypertension by this definition is 12.5% in one year, or 33.0% extrapolating to 3 years. Extrapolating the HPT rate to 3.5 years yields an estimated event rate of 34.5% in the control group for this study.
 - b. The HPT data are based on a single visit, and may thus

overestimate the incidence of hypertension. An event rate of 29.7% was derived from the estimates of the one year event rate in TOHP Phase I and simulations using the gamma distribution with parameters based on NHANES II data (44) and the event rates in HPT (38). This assumes blood pressure measurements over 3 visits to determine the development of hypertension, as in the current study. A 10% loss to follow-up is assumed, reducing the event rate to 26.7% in the control group.

- 2. The expected reductions in the event rate are 30% for weight loss, 20% for sodium restriction, and 40% for weight loss plus sodium restriction. These expected reductions were based on the results of Phase I and other trials of primary prevention (HPT, PPH, and HIP). This assumes subadditivity of effects. Under the additive model the risk reduction in the combined intervention group would be 44%.
- 3. The sample size is estimated to be 2250 subjects as outlined above.

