 The number in each comparison group will be 1125 for the overall weight loss and sodium restriction hypotheses and 562 for the combined intervention versus control hypothesis.
- 4. A Bonferoni adjustment for three comparisons is made.
- 5. The power is calculated for the logrank test using the following formula (45):

Power =
$$\Phi$$
 [\sqrt{d} |1- θ / 1+ θ | - z_{α}] where
$$d = N(2 - p_{o} - p_{1})$$

$$\theta = \ln p_{o} / \ln p_{1}$$

and

N = number in each group

 \mathbf{p}_{\circ} = probability of remaining normotensive in the comparison group

 p_1 = probability of remaining normotensive in the active

group

 $z_{\alpha} = 2.394$

Estimates of power are given in Table 5. The relative risks listed in the table represent the average risk reductions for the main effects of the single interventions when using all four groups. Using these assumptions the power to determine the effectiveness of weight loss alone is at least 93.6% for this endpoint while that for sodium restriction is no more than 65.4%. The power is over 97% to detect the hypothesized difference between the combined intervention and control groups in development of hypertension. This study, however, has little power to detect differences between the combined intervention and either single intervention group with these expected reductions. The power to detect a difference between the combined and sodium restriction group is at most 62%, while that for the combined vs. weight loss group is 16%.

The revised primary categorical endpoint is the development of systolic or diastolic hypertension, defined as DBP $_{2}$ 90 mmHg, or SBP $_{2}$ 140 mmHg or taking antihypertensive medication. The HPT saw an incidence rate of 38.7% for this endpoint among high weight controls over 3 years. Extrapolating to 3.5 years leads to a rate of 43.5%. All other assumptions remain the same. The increase in monitoring for systolic blood pressure of 140-159 mmHg is likely to increase the incidence of this endpoint. Simulations were performed using a random effects model and the parameters given in sections A and B above and with the additional assumptions of population means of 128.4 mmHg for SBP and 82.0 mmHg for DBP, and a correlation of SBP and DBP of 0.80. An effect of adjustment to the study situation was also assumed (a lowering of mean BP in addition to the expected regression to the mean). These simulations suggest that the incidence of the combined endpoint may

TOHP II Protocol 12/15/92

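### The single-step Bonferroni rule over three hypotheses is valid but needlessly inefficient: Holm's step-down holds the same family-wise 0.05 and would raise sodium power for the hypertension endpoints by about 7 to 16 points

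*Protocol*

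**What the plan says.** Sample Size and Power, part A, defines three hypotheses: the weight-loss main effect, the sodium main effect, and combined intervention versus control. Item A.4 reads "A Bonferoni adjustment is made based on the fact that 3 comparisons will be examined", and item A.5 sets the critical value at 2.394. Part B carries the adjustment over to systolic pressure. Item C.4 repeats it for the hypertension endpoints: "A Bonferoni adjustment for three comparisons is made". Item C.5 again uses 2.394, in a logrank power formula.

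The resulting sodium powers are in Tables 5 and 6:

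- **Diastolic hypertension:** 65.4% or 48.0%, depending on the assumed event rate. The text says of weight loss that power is at least 93.6%, "while that for sodium restriction is no more than 65.4" per cent.
- **Combined systolic or diastolic hypertension** (the primary categorical endpoint): 82.5% or 87.0%.

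In the same tables weight loss has 93.6% to 100% and combined versus control 97.5% to 100%.

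Data Analyses names the tests for each hypothesis but gives no multiplicity rule. Single-step Bonferroni is therefore the only rule in the document.

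**The concern.** Bonferroni holds every hypothesis at two-sided 0.05/3, whatever happens to the others. Holm's procedure tests the smallest p-value at 0.05/3, the next at 0.05/2 and the last at 0.05, and stops at the first non-rejection. It controls the family-wise error strongly at 0.05 under any dependence between the tests, and it rejects everything that Bonferroni rejects.

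The two methods differ most when some hypotheses are almost sure to be rejected and another is marginal. Tables 5 and 6 show that pattern: two tests near certainty and sodium well behind. What is at stake is sodium power that could be had without a single extra participant.

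**Working it through.** **Inputs (Sample Size and Power, part C)**

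- Group sizes: "The number in each comparison group will be 1125 for the overall weight loss and sodium restriction hypotheses and 562 for the combined intervention".
- Effects: "The expected reductions in the event rate are 30% for weight loss, 20% for sodium restriction, and 40% for weight loss plus sodium restriction".
- Diastolic hypertension, first control rate: "Extrapolating the HPT rate to 3.5 years yields an estimated event rate of 34.5% in the control group for this study".
- Diastolic hypertension, second control rate, after 10% loss: "reducing the event rate to 26.7% in the control group".
- Combined hypertension control rates: 43.5%, and 47.2% with increased monitoring.
- Critical value 2.394 = z(1 − 0.05/6), that is, two-sided 0.05/3. The sidedness is inferred from the value.

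**Step 1: reproduce the protocol's figure.** The C.5 formula is power = Φ[√d·|1−θ|/(1+θ) − z], with d = N(2−p0−p1) and θ = ln p0/ln p1. At a control rate of 34.5% the arm rates are Wt 24.15%, Na 27.6% and WtNa 20.7%. The sodium margins are:

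- without sodium: (34.5 + 24.15)/2 = 29.325%, so p0 = 0.70675
- with sodium: (27.6 + 20.7)/2 = 24.15%, so p1 = 0.7585

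The average reduction is 1 − 24.15/29.325 = 17.6%, which Table 5 prints as 18%. Then d = 1125 × 0.53475 = 601.6, θ = 1.2557, and the expected z is √601.6 × 0.2557/2.2557 = 2.780. Power is Φ(2.780 − 2.394) = 65.0%, against 65.4% printed. All entries of Tables 5 and 6 reproduce within 1.0 point.

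**Step 2: ceiling under Holm.** If both other hypotheses are rejected, sodium is tested at 1.960, and power is Φ(2.780 − 1.960) = 79.4%.

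**Step 3: Holm by simulation.** I used 1,000,000 triples of z statistics with cut-offs 2.394, 2.241 and 1.960. At the 34.5% rate the means for weight, sodium and combined are 4.62, 2.78 and 5.14. The two main effects are independent, and combined versus control is correlated 1/√2 = 0.71 with each. Sodium power (%):

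| Endpoint, control rate | Printed | Formula at 2.394 | Ceiling at 1.960 | Holm (simulated) | Gain over simulated Bonferroni |
|---|---|---|---|---|---|
| Diastolic, 34.5% | 65.4 | 65.0 | 79.4 | 79.4 | 14.3 |
| Diastolic, 26.7% | 48.0 | 48.1 | 65.1 | 64.6 | 16.4 |
| Combined, 43.5% | 82.5 | 81.5 | 90.8 | 90.9 | 9.3 |
| Combined, 47.2% | 87.0 | 86.7 | 93.9 | 93.9 | 7.1 |

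Simulation error is below 0.1 point. Treating the third test as independent changes the gains by at most 0.2 point.

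**Step 4: error control.** Under the global null, simulated family-wise error is 4.1% for both methods. With only the sodium null true (expected z of 4.5 for weight and 3.2 for combined), Holm rejects sodium 4.0% of the time.

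**Step 5: how far the gain depends on the other effects.** With no weight effect, a sodium mean of 2.78 and a combined mean of 2.78/√2, sodium power is 65.0% under Bonferroni and 66.0% under Holm. There is no loss, but almost no gain.

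**Step 6: primary DBP change.** The expected z is Δ/(σ√(2/n)), with n = 1125 × (1 − 0.311) = 775.1 per side for a main effect and 562.5 × 0.689 = 387.6 for combined versus control. This gives 97.5% at 1.5 mmHg for a main effect (Table 1: 97.5) and 91.4% at 1.0 mmHg with SD 5.24 (Table 2: 91.4). The protocol gives no arm-specific DBP effects for power, so those below are assumptions. The sodium main effect is (Na + WtNa − Wt)/2.

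| Assumed Wt/Na/WtNa (mmHg) | Sodium main effect | SD | Bonferroni % | Holm % | Gain |
|---|---|---|---|---|---|
| 1.5/1.0/2.0 | 0.75 | 6.78 | 41.4 | 57.7 | 16.3 |
| 1.5/1.0/2.0 | 0.75 | 5.24 | 66.4 | 80.4 | 14.0 |
| 2.0/1.5/2.5 | 1.00 | 6.78 | 69.4 | 82.6 | 13.2 |
| 2.0/1.5/2.5 | 1.00 | 5.24 | 91.4 | 96.4 | 5.0 |

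**The case against.** The strongest reply is that nothing here is wrong. Bonferroni is valid, 2.394 is the correct value for three comparisons, and the tables follow from it. That stands, and it limits the point to efficiency.

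Second, A.4 and C.4 are inputs to power calculations. Data Analyses fixes no rule, so planning with Bonferroni and analysing with Holm would contradict nothing in the text. That also stands: the protocol does not show that the final tests will be single-step. It does mean that the printed sodium powers describe the weaker procedure, and that no other procedure is stated.

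Third, a reader might infer that sodium is an under-powered primary aim. The documents do not support this. The primary sodium aim concerns DBP, where Tables 1 and 2 give sodium the same power as weight loss at any given difference, and the protocol calls power for both main hypotheses more than adequate. At an equal difference, the weaker DBP test is combined versus control (75.3% at 1.5 mmHg to termination). The low sodium figures, 65.4% and 48.0%, belong to diastolic hypertension, which part C makes a secondary look. For the primary categorical endpoint sodium already exceeds 80%.

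Fourth, the 1.5/1.0/2.0 mmHg example implies a sodium main effect of only 0.75 mmHg, whereas the Background cites a DBP decline of about 1 to 2 mmHg with sodium reduction. The DBP gains therefore show a range and are not a forecast.

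**Conclusion.** The point holds as an avoidable loss of efficiency. Holm gives the same family-wise protection and cannot do worse. Under the protocol's own event rates and 30/20/40% reductions, sodium gains about 7 to 9 points on the primary categorical endpoint and 14 to 16 points on diastolic hypertension, where it still stays below 80%. These gains assume that the weight and combined effects are real. For primary DBP change the gain is about 5 to 16 points under the assumed arm effects, and the protocol alone cannot narrow that. It would be wrong to conclude that the stated powers are incorrect or that the trial's primary sodium test is under-powered.

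**What to change.** Before any unblinded analysis, replace the single-step adjustment in A.4, B and C.4 with Holm's step-down across the three hypotheses, applied separately within each endpoint: smallest p-value at 0.05/3, next at 0.05/2, last at 0.05, stopping at the first non-rejection. State the same rule in Data Analyses. Restate sodium power in Tables 5 and 6 and the accompanying text by simulation, giving the assumed weight and combined effects on which it depends. If DBP power is restated too, give the assumed arm effects.

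There are two costs. Simultaneous confidence intervals matching Holm are less simple than Bonferroni intervals. Holm power depends on all three tests jointly, so it needs a short simulation in place of the closed formulas. Sample size, data collection and conduct do not change.

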This design allows us to test the overall effect of weight loss and the overall effect of sodium restriction. The effect of the combined intervention can also be tested. In addition, we will examine the effect of the combined intervention as compared to weight loss, sodium restriction and the absence of weight loss and sodium restriction.

All nine clinics will randomize participants into all four arms and subjects will be distributed equally among the three treatment groups and the control

group (1/4 each). Randomization will be stratified by clinic to insure even distributions into the four treatment groups at each of the clinical centers.

SAMPLE SIZE AND POWER

- A. The hypotheses to be tested in this factorial design are 1) the overall effect of weight loss (i.e., groups A and B vs. groups C and D); 2) the overall effect of sodium restriction (i.e., groups A and C vs. groups B and D); and 3) the effect of the combined intervention (i.e., group A vs. group D). The primary endpoint for testing these hypotheses will be change in mean diastolic blood pressure (DBP) both from baseline to termination BP and from baseline to the average of all DBP's from 6 months to 36 months. The assumptions for calculating the necessary sample size for these continuous endpoints are as follows:
 - 1. Baseline blood pressure measurements will be taken at 3 visits with three measurements per visit. Follow-up BP measurements will be taken over 3 visits at 18 and 36 months, and 1 visit at 6, 12, 24 and 30 months, each with 3 measurements per visit. The termination BP is defined as the BP at 36 months or before starting BP medication, which will also be based on 3 visits with 3 measurements per visit. The blood pressure measure for an individual is thus an average of nine readings at baseline and at termination. The variance of the change from baseline (x_1) to termination (x_2) can be written as:

$$\sigma_1^2 = V(x_2 - x_1) = 2\sigma_p^2(1 - \rho_{0,36}) + 2(\sigma_A^2 + \sigma_e^2/k)/n$$

where σ_{p}^{2} = between-person variance

 σ_{λ}^{2} = between-visit variance

 $\sigma_{\rm e}^2$ = within-visit variance

n = number of visits = 3

k = number of measurements per visit = 3

 $\rho_{\text{i,j}}$ = tracking correlation of the individual's true blood $pressure\ mean\ from\ time\ i\ to\ time\ j,\ with\ 0\ representing$ baseline

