The variance of the change from baseline (x_1) to the unweighted average of the time-specific means at 6 months through 36 months (x_3) can be written as:

can be written as:
$$\sigma_{2}^{2} = V(x_{3} - x_{1}) = (\sum (\sigma_{p}^{2} + \sigma_{a}^{2}/n_{i} + \sigma_{e}^{2}/k_{i}n_{i}) + 2\sum \rho_{i,j}\sigma_{p}^{2})/36$$

$$i$$

+
$$(\sigma_{p}^{2} + \sigma_{a}^{2}/n_{o} + \sigma_{e}^{2}/k_{o}n_{o}) - \sigma_{p}^{2} \Sigma \rho_{o,i}/3$$

where i and j represent the 6 measurement times from 6 months through 36 months

 n_i = the number of visits at time i

 $\ensuremath{k_{\scriptscriptstyle i}}$ = the number of measurements per visit at time i (=3) and all summations are over times 6 to 36 months.

The following parameter estimates are applied:

a) The variance components were based on race and gender specific estimates from a population of 991 individuals aged 30-69 years (41). These were combined by taking weighted averages using the age, sex and race distribution of the Phase I participants. This population was 30% female, 15% black, with 80% aged 30-49 and 20% aged 50-54. The average variance components are:

$$\sigma_{p}^{2} = 100.4$$

$$\sigma_{a}^{2} = 27.3$$

$$\sigma_{e}^{2} = 7.6$$

b) Tracking correlations of 0.58 (42) for DBPs taken four years apart and 0.85 (43) for those taken one year apart have been published. For any time interval the relationship of the true correlation (ρ_t) to these observed correlations (ρ_o) is a function

of the number of visits (n) and measurements per visit (k) as follows:

$$\rho_{t} = \rho_{o} \times (\sigma_{p}^{2} + \sigma_{A}^{2}/n + \sigma_{e}^{2}/nk)/\sigma_{p}^{2}$$

with the various components as defined previously. These data suggest true 4-year and 1-year correlations of 0.85 and 0.91.

Interpolating from these results, we estimate that the true tracking correlations over 6, 12, 18, 24, 30 and 36 months are 0.95, 0.91, 0.90, 0.89, 0.88, and 0.87, respectively.

Using the above parameters, the estimated variance of DBP change from baseline to termination is 6.78^2 within each treatment group. The estimated variance of DBP change from baseline to the average of all follow-up visits is 5.24^2 .

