The endpoint of diastolic hypertension (sustained DBP $_{2}90$ mmHg) occurs if DBP is $_{2}90$ mmHg based on nine readings over three visits at any follow-up point. At the 18- and 36-month follow-up points, all participants come for three visits. At the 6-, 12-, 24-, 30-, 42-, and 48-month follow-up points, all participants come for at least one visit consisting of three BP measurements. If the mean of three DBP is $_{2}90$ mmHg at this visit, then the participant returns for a second visit seven to ten days later. If the mean of six DBP is $_{2}90$ mmHg, then the participant returns for a third visit seven to ten days later. If the mean of nine DBP is $_{2}90$ mmHg after the third visit, then the participant is considered to have diastolic hypertension and is asked to notify his/her physician.

The endpoint of systolic hypertension,* (see 12/03/92 modification below) defined as sustained SBP >160 mmHg, occurs if SBP is $_{\geq}160$ mmHg based on nine readings over three visits at any follow-up point. At the 18- and 36-month follow-up points, all participants come for three visits. At the 6-, 12-, 24-, 30-, 42- and 48-month follow-up points, all participants come for at least one visit consisting of three BP measurements. If the mean of three SBP is $_{\geq}160$ mmHg, then the participant returns for a second visit seven to ten days

later. If the mean of six SBP is $_{\geq}160$ mmHg, then the participant returns for a third visit seven to ten days later. If the mean of nine SBP is $_{\geq}160$ mmHg after the third visit, then the participant is considered to have systolic hypertension and is asked to notify his/her physician. The endpoint of systolic hypertension, alternatively defined as sustained SBP $_{\geq}140$ mmHg, occurs if the mean of nine SBP is $_{\geq}140$ mmHg at the 18- and 36-month follow-up points, since at these follow-up visits participants come for all three visits without regard to cutpoints based on SBP $_{\geq}160$ mmHg as the endpoint. The endpoint of SBP $_{\geq}140$ mmHg also occurs if the criteria for SBP $_{\geq}160$ mmHg are met.

12/03/92 Modification:

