To assess the effects of weight loss, sodium restriction, and their combination, the mean changes in DBP at 36 months in the various groups will be compared. Additionally, the average of all BPs obtained during the trial in the various groups will be compared. The analysis of variance for a two-by-two factorial design will be used to test the main effects of weight loss and of sodium restriction. Multiple regression analyses will be performed to adjust for other covariates, such as age, sex, and initial weight and urinary sodium. To reduce the impact of regression to the mean and to improve the error variance, as well as to adjust for any imbalance, mean initial DBP will also be included in the model. To compare DBP changes in two of the four groups, such as the combined intervention versus placebo, comparisons of means

with a t-test and multiple regression analyses will similarly be used. These methods can also be used to explore the effect of the combined intervention compared to a single intervention such as weight loss alone. More sophisticated methods of longitudinal data analysis such as computing slopes over time or the use of autoregressive models will be used to explore more complex changes in DBP over time in the various treatment groups (48-50).

Because the effect of treatment may not be uniform across all members of a group, we will also examine the distribution of blood pressure changes. Should these appear not to be normally distributed, we will perform nonparametric tests of significance. To examine the effect of actual compliance to the treatment regimen, we will consider change in DBP as a function of actual change in weight and urinary sodium. This is of particular importance because some members of the control group may seek to implement the intervention strategies on their own.

Censoring of this continuous variable due to incidence of hypertension is a potential problem in this analysis. Once antihypertensive medications are prescribed, blood pressure readings become biased in those subjects who should have the highest levels. For this reason we will attempt to acquire and use termination blood pressures obtained prior to initiation of antihypertensive therapy. Furthermore, individuals who are told they are hypertensive may begin some nonmedical intervention; such as weight loss, on their own, perhaps under the advise of their physicians, even if they do not take medications.

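### The analysis section describes the averaged DBP outcome differently from the endpoint that was defined and powered, and no rule keeps on-drug readings out of it

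*Protocol*

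**What the plan says.** SAMPLE SIZE AND POWER, section A, gives the primary endpoint two forms: DBP change to the termination BP, and DBP change "from baseline to the average of all DBP's from 6 months to 36 months". The variance derivation in A.1 defines the second form as "the unweighted average of the time-specific means at 6 months through 36 months", and its formula sums over six times: "where i and j represent the 6 measurement times from 6 months through 36 months". The visit plan is one visit at 6, 12, 24 and 30 months and three at 18 and 36. Table 2 gives the power.

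DATA ANALYSES first compares mean DBP changes at 36 months. It then adds that "the average of all BPs obtained during the trial in the various groups will be compared". That sentence has no 6-36 month window, no equal weighting by time point and no reference to change from baseline.

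The trial also collects readings outside the powered definition. Under ENDPOINTS, a high mean at a one-visit time point means that "then the participant returns for a second visit seven to ten days later", and possibly a third visit follows. There are 42- and 48-month visits (the timetable shows 70% and 33% of participants) and safety-monitoring visits.

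On drug treatment, DATA ANALYSES states: "Once antihypertensive medications are prescribed, blood pressure readings become biased in those subjects who should have the highest levels". The remedy given there, and the definitions in SAMPLE SIZE AND POWER (section A for DBP, section B for SBP), attach the pre-drug limit to the termination BP. No sentence attaches it to the average.

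**The concern.** An analyst who follows the DATA ANALYSES sentence literally computes a different quantity from the one in Table 2. That matters because the Protocol leans on the average: at 1.5 mmHg, combined-versus-control power is 75.3% for the termination change (Table 1) and 94.4% for the average (Table 2).

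Three kinds of extra reading could enter: repeat visits that happen only because a first reading was high, 42- and 48-month readings from part of the cohort, and readings on antihypertensive drugs. The third is the serious one. Drug treatment lowers the highest pressures, and more control participants are expected to reach that point, so including such readings narrows the difference between arms.

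**Working it through.** **1. Reproduce Table 2.** Inputs from SAMPLE SIZE AND POWER, section A: SD 5.24 mmHg, z = 2.394 (Bonferroni for three comparisons), 31.1% censored, 2250/4 = 562.5 per group.

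Power = Φ(Δ / (SD·√(2/(N(1 − Pc)))) − 2.394)

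N(1 − Pc) = 562.5 × 0.689 = 387.6, so the standard error is 5.24 × √(2/387.6) = 0.376. At Δ = 1.2: 1.2/0.376 = 3.188, less 2.394 gives 0.794, and Φ = 78.6%. At 1.0 and 1.5 mmHg the results are 60.4% and 94.4%. All three match Table 2. The A.1 variance formula gives an SD of 5.19 against the stated 5.24, which moves power by one point or less.

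The table therefore assumes 31.1% censoring, which includes incident hypertension. It does not assume that treated hypertensives keep contributing readings.

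**2. Simulate the extra readings.** Inputs from the Protocol: DBP variance components 100.4, 27.3 and 7.6; the tracking correlations; population mean 82.0; entry at 83-89 mmHg; the repeat-visit rule. The true effect is 1.5 mmHg. A lowering of mean DBP as participants adjust to the study is assumed (0-4 mmHg across runs). Scheduled visits alone, with no drug treatment, return 1.50 mmHg with SD 4.84.

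*Triggered repeats.* Pooling all readings gives about 1.52 mmHg, so there is no shrinkage. Placing the repeats inside each time-specific mean gives 1.42 mmHg, but the SD drops to 4.55. The standardized effect is 1.42/4.55 = 0.31, the same as 1.50/4.84 = 0.31, so power is unchanged.

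*42 and 48 months.* If the effect persists, the pooled result is about 1.52 mmHg. If it halves after 36 months (assumed), the result is about 1.44 mmHg.

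*On-drug readings at scheduled visits.* Neither the share who start drugs nor the size of the fall is in the Protocol. Both are assumptions.

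| Share starting drugs, DBP fall | Difference for a true 1.5 | Loss | Power at 1.2, SD held at 5.24 | Power at 1.2, lower SD allowed |
|---|---|---|---|---|
| none | 1.50 | 0% | 79% | 79% |
| 25%, 5 mmHg | 1.43 | 5% | 74% | 77% |
| 50%, 8 mmHg | 1.31 | 13% | 65% | 72% |
| 75%, 10 mmHg | 1.15 | 23% | 52% | 64% |

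The fourth column scales 1.2 by the ratio to 1.5. For example, 1.2 × 1.31/1.5 = 1.048; 1.048/0.376 = 2.784; less 2.394 gives 0.39, and Φ = 65%. The last column is the fair one, because on-drug readings also compress the spread. A repeat of the simulation gave 1.43, 1.29 and 1.11 mmHg, with power of 77%, 71% and 61%.

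**3. Drop readings after drug start.** The same simulation gives about 1.54-1.63 mmHg for a true 1.5, and power at 1.2 mmHg returns to about 77%.

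**The case against.** The strongest reply is that the sentence is shorthand for an endpoint defined elsewhere. SAMPLE SIZE AND POWER itself uses loose names for the average, while the formula and the Table 2 title fix 6 to 36 months. FOLLOW-UP places the final collection for the continuous endpoint at 36 months, and the primary aims are framed over 36 months. Section A also remarks that participants who start medication will have given partial data, especially in the analysis of all follow-up data, which makes sense only if later readings are dropped. DATA ANALYSES discusses on-drug bias as censoring. This is good evidence of intent, and it makes the 42/48-month reading unlikely. It does not supply a rule: no sentence says that the average stops at the start of medication.

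The on-drug gap is also not created by the DATA ANALYSES sentence. Section A has no drug exclusion for the average either, and the 6-36 month mean is cut by a similar amount if on-drug readings enter. That is correct, and it is why restoring the definition alone would not be enough.

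The status of the average is mixed. Section A names it as primary, but ENDPOINTS gives termination change as the outcome of primary interest, and DATA ANALYSES bases the primary analysis on termination BP and introduces the average as an addition.

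A reader might infer that every kind of extra reading shrinks the effect and favours a null result. The check does not support that for triggered repeats, and supports it for 42/48-month readings only if the effect wanes. A reader might also take the fixed-SD power losses at face value; they overstate the damage.

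**Conclusion.** The conflict is real and confined to wording: DATA ANALYSES describes an average without the window, weighting or baseline reference of the endpoint that was defined and powered. The material consequence is the missing pre-drug rule for the average, a gap shared by SAMPLE SIZE AND POWER. Under the assumed drug-start shares and falls, the loss runs from 5% to 23% of the effect, and from about 2 to 15 points of combined-versus-control power at 1.2 mmHg. At the mild end the effect on power is negligible; at the other end it is substantial. The documents do not show that the trial intended to use on-drug readings, only that nothing written prevents it. Since termination BP leads elsewhere in the Protocol, this should be corrected but does not undermine the main analysis.

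**What to change.** In DATA ANALYSES, replace the sentence with the section A definition: for each participant, the change in DBP from baseline to the unweighted mean of the scheduled time-specific means at 6, 12, 18, 24, 30 and 36 months. Use only the first visit at 6, 12, 24 and 30 months and the three scheduled visits at 18 and 36, so that the number of readings does not depend on the outcome. Add that no reading taken after the start of antihypertensive medication enters the average, as is already the rule for termination BP, and state the same in section A. Section B uses the same construction for SBP and should match. Triggered repeats then serve the hypertension endpoints.

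The cost is a sentence or two and no new data. A few readings go unused. Participants who start drugs contribute partial data, which moves the estimate slightly upward: 1.54-1.63 mmHg for a true 1.5, or 3% to 9%. The rule therefore reduces the bias without removing it entirely.
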